7.1. Adverse Event Definitions

An adverse event is any untoward medical occurrence associated with the use of a drug in humans, whether or not considered drug-related. An adverse event can be any unfavorable and unintended sign or symptom, including abnormal laboratory findings, or disease, that is temporally associated with the use of a drug, and does not imply any judgment about causality. An adverse reaction is any event that is caused by a drug or device, ie, possibly-, probably-, or definitely-related to the use of the drug or device.

Except as otherwise explicitly defined within this section, **this also includes all events of clinical deterioration such as tumor relapse, recurrence, or upstaging, or new cancers.**

Within the scope of this study and protocol, adverse device effects, ie, events that have a serious adverse effect on health or safety or any life-threatening problem or death caused by, or associated with, a device may be referred to as "serious adverse events (SAEs)."

Serious adverse events (SAEs) are defined per the FDA definition at [21CFR§312.32\(a\)](#) and [ICH GCP E6](#). An adverse event is considered "serious" if, in the opinion of the PD, investigator, or sponsor, it results in ANY of the following.

- Death
- Life-threatening adverse event with an **actual and immediate risk of death** [21CFR§312.32(a)]
- In-patient hospitalization or prolongation of existing hospitalization, except planned hospitalization or hospitalization only for study conduct will not be considered SAEs. Note that the per-protocol cryoablation procedure will not be considered an SAE hospitalization, even if the patient stays in the clinic overnight.
- A persistent or significant incapacity or substantial disruption of the ability to conduct normal life functions
- A congenital anomaly/birth defect
- Event jeopardizes the subject and may require medical or surgical intervention to prevent one of the outcomes listed here

7.2. **Classification of Adverse Events**

7.2.1. **Severity of Event**

NCI CTCAE version 5.0 is used to assess the severity of adverse events in this study.

7.2.2. **Adverse Event Attribution to Intervention or Study**

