GS inhibition may affect the intestinal tract epithelium (Barker, 2007; Kurokawa, 2020), villus lacteals (Norden, 2021), and enteric nervous system (Willem, 2016; Barrenschee, 2015), and lead to diarrhea, which could in turn lead to loss of electrolytes. In addition, Notch signaling in the nephron is responsible for the maintenance of the balance of epithelial cell type diversity and epithelial repair (Mukherjee, Fogarty, et al, 2019), and

disruption of this balance could lead to altered ability of the kidney to adapt to impaired electrolyte imbalances (Mukherjee, deRiso, et al., 2019).

Electrolyte abnormalities occurred in participants taking nirogacestat in Study NIR-DT-301. This included hypophosphatemia (42%) and hypokalemia (12%). Grade 3 events occurred in 3% and 1% of participants, respectively. Phosphate and potassium levels should be monitored regularly and supplemented as necessary. See also Section 5.6 Dose Modifications.

- **Elevated Liver Transaminases:**

Effects on hepatic function emerged as an AE of special interest for nirogacestat based on observations of mild hepatic vacuolation in nonclinical studies in rats, and transient transaminase elevations in early clinical studies with nirogacestat.

ALT or AST elevations occurred in 20% of participants who received nirogacestat in Study NIR-DT-301. Grade 3 ALT or AST elevations (> 5 times ULN) occurred in 3% of participants. The majority of ALT or AST elevations were Grade 1 (> ULN to 3 times ULN), occurred within the first month of treatment, and resolved spontaneously without dose modification. Liver function tests should be monitored regularly. See Section 5.6 Dose Modifications and Section 13.8 Appendix G Liver Safety: Suggested Actions and Follow-up Assessments.

- **Embryo-fetal Toxicity:**

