7.4. Adverse Event Monitoring and Collection

Untoward medical events experienced by a study subject receiving an interventional drug, device, or procedure, or within **30** days after such treatment, will be considered an adverse event (AE), regardless of whether or not considered drug-related. All events of disease progression or second cancer will be recorded as a serious adverse event (SAE) using the Preferred Term appropriate for the clinical finding.

All adverse events Grade 1 and higher will be collected and recorded as AEs.

In addition, laboratory values without a requirement for intervention, clinical consequence, or outcome will not be considered adverse events, unless deemed serious.

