7.5.3. Other Adverse Events of Special Interest

Adverse events of special interest (AESI) are selected non-serious and serious AEs that must be reported regardless of relationship to study treatment. Refer to Table 8 for the AESIs identified for this study. AESIs will be followed until resolution or return to baseline.

Serious AESIs will be reported to SpringWorks Safety at ([contact]) according to procedures and timeline (Section 7.6)

Non-serious AESIs must be reported to SpringWorks Safety at [contact] as soon as possible, but no later than 30 calendar days of awareness.

Following medical evaluation, SpringWorks may request study site to provide supplemental information (such as medical history, concomitant medications, investigations, etc.) about the event. Please note this table lists known AESI; additional events may be identified during the course of the study.

Table 8. Adverse Events of Special Interest

Elevated Liver Enzymes (reported as AESI if Grade ≥ 2, per CTCAE v. 5)

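### Section 7.4 denies adverse-event status to some laboratory changes that Table 8 requires to be reported as adverse events of special interest, and nothing says which rule prevails

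*Protocol*

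**What the plan says.** Four places in the protocol bear on whether an abnormal laboratory value is an adverse event (AE).

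- Section 7.1 gives the general definition: "An adverse event can be any unfavorable and unintended sign or symptom, including abnormal laboratory findings, or disease". It sets no condition about treatment or consequence.
- Section 7.4 first says "All adverse events Grade 1 and higher will be collected and recorded as AEs", and in the next paragraph that "laboratory values without a requirement for intervention, clinical consequence, or outcome will not be considered adverse events, unless deemed serious".
- Section 7.4.1 asks staff to record significant laboratory findings, but allows for exceptions made elsewhere in the protocol.
- Section 7.5.3 says: "Adverse events of special interest (AESI) are selected non-serious and serious AEs that must be reported regardless of relationship to study treatment". Its Table 8 opens with "Elevated Liver Enzymes (reported as AESI if Grade ≥ 2, per CTCAE v. 5" and lists AST, ALT, alkaline phosphatase and total bilirubin. Non-serious AESIs go to the drug supplier within 30 calendar days of awareness.

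Section 10.2.2.6 then tabulates AEs by grade, severity, status and relationship, for all subjects who started treatment.

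**The concern.** Section 7.5.3 makes an AESI a subset of AEs. If 7.4 says that a given value is not an AE, that value has no way into the AESI stream, yet Table 8 requires it there. Two coordinators could handle the same Grade 2 result differently and both be following the protocol.

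Safety is a secondary objective, and raised transaminases are a named important identified risk. Section 7.3 also says that it is unknown whether the combination with cryoablation carries additional risk. The non-serious AESI report is the stated route by which low-grade liver findings reach someone outside the site, so an ambiguity about what enters it matters even in a small trial. The same ambiguity decides which low-grade laboratory changes appear in the all-grade AE table.

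**Working it through.** No design figure depends on this rule, so there is none to reproduce. The check is a reading of the rules against two cases, followed by a rough size.

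**Case A: isolated Grade 2 AST rise, non-serious, no symptoms, no treatment given.**
- Section 7.1: an abnormal laboratory finding, so an AE.
- Section 7.4: no intervention, consequence or outcome, and not serious, so not an AE.
- Table 8: Grade 2 AST, so an AESI. By the 7.5.3 definition it must then be an AE.
- Section 7.4.1: record if significant, unless the protocol says otherwise. That returns the reader to the 7.4 exclusion.
- Appendix G: every listed stopping criterion and both action tiers require an ALT elevation, so nothing is triggered.

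The rules give opposite answers. The same holds for isolated alkaline phosphatase or total bilirubin. (Figure 1 is not available in the text; this relies on Appendix G.)

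**Case B: isolated Grade 2 ALT rise.** Section 7.3.1 puts Grade 1 at up to 3 times the upper limit of normal and Grade 3 above 5 times, so Grade 2 lies between. For ALT at or above 3 times the limit, with bilirubin and INR below their thresholds, Appendix G suggests repeat tests within 24 to 72 hours and then weekly monitoring. That is arguably a clinical consequence, so the 7.4 exclusion may not apply. The gap is less clear here than in Case A.

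**Size, from the NIR-DT-301 figures in Section 7.3.1 and Tables 1 and 6.**
- The table percentages check: ALT 12/69 = 17.4% (stated 17%), AST 11/69 = 15.9% (stated 16%), Grade 3 for each 2/69 = 2.9% (stated 3%).
- Any ALT or AST elevation: 20% of 69 = 13.8, about 14 participants.
- Grade 3: about 2 participants.
- Most elevations were Grade 1. Assumption: more than half of the affected participants, so at least 8 of 14.
- Grade 2: between 0 and 14 − 8 − 2 = 4 participants, that is 0 to 4/69 = 5.8%.
- Expected here: 0 to 20 × 4/69 = 1.2 in 20 subjects, or 0 to 23 × 4/69 = 1.3 in 23.
- Chance of at least one such subject at the upper end: 1 − (1 − 4/69)^n, which is 0.70 for n = 20 and 0.75 for n = 23.

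Only the untreated, symptom-free part of these would fall into the conflict. Grade 2 alkaline phosphatase and bilirubin elevations come on top, and the documents give no NIR-DT-301 rate for them.

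**The case against.** The best defence is that there is little real conflict. A general definition in 7.1 may legitimately be narrowed by 7.4, and the Grade 1 collection rule then applies to whatever still counts as an AE. Table 8 is the more specific rule and is mandatory, so a sensible reader would let it prevail. The values themselves are not lost: chemistry is drawn every cycle through Cycle 6 and every third cycle afterwards, and laboratory reports are source documents.

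The point about 7.1 stands, and so does the point that the protocol contradicts itself rather than plainly discarding these events. But no sentence gives Table 8 priority, and 7.4.1 points the other way. A value kept in a laboratory report does not by itself produce an AESI report or an entry in the AE table.

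Stronger readings are tempting, and the documents do not support them.

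- A reader might infer that laboratory AE rates here cannot be compared with nirogacestat alone. No AE-rate comparison is planned. The synopsis mentions historical controls beside response and progression measures, safety is tabulated descriptively, and the recording rule of the historical study is not given.
- A reader might infer that the recorded ALT/AST rate would fall from 20% to the Grade 3 rate of 3%. Section 7.3.1 does say that most elevations "occurred within the first month of treatment, and resolved spontaneously without dose modification", but the same sentence says they were Grade 1, below the Table 8 threshold. Resolving without dose modification is also not the same as having no intervention, consequence or outcome.
- A reader might take an untreated Grade 2 ALT rise as the leading example. Appendix G weakens it, as Case B shows.
- A reader might infer that the data and safety monitoring committee would lose an early signal. Its stated review covers serious adverse events and protocol deviations, so these values were not in that stream.

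**Conclusion.** The contradiction between Section 7.4 and Table 8 is real and follows from the wording alone. A non-serious, asymptomatic, untreated Grade 2 elevation is a required AESI and also not an AE. It is clearest for AST, alkaline phosphatase and bilirubin.

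The expected size is small: about 0 to 1.3 of 23 subjects with a Grade 2 ALT or AST rise. That range assumes that the NIR-DT-301 rates carry over and that the Grade 1 majority can be counted by participant. The all-grade table in 10.2.2.6 could also under-count low-grade laboratory changes, but the documents do not give the share that needs no action, so no figure can be put on it. The registered safety outcome counts related events of Grade 3 or higher and should be little affected for ALT, because ALT at or above 5 times the upper limit meets an Appendix G stopping criterion.

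**What to change.** Reconcile the two sections with one clause in 7.4: laboratory abnormalities that meet Table 8 are recorded as AEs and reported as AESIs whether or not any action is taken. The rest of the 7.4 exclusion can stay.

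The cost is a short amendment, a few more AE entries and possibly one or two more non-serious AESI reports. All would come from chemistry results that the Section 6.1 schedule already collects. No visit, test or treatment rule changes.

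Two wider changes are optional and are not needed to remove the contradiction. One is to extend the exemption to phosphate and potassium, which are named risks but are not in Table 8. The other is to delete the exclusion so that 7.1 governs.

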7.4.1. Case Report Forms for Adverse Event Reporting

Both SAEs and non-serious adverse events will be described in source documentation and listed on study-specific Case Report Forms (CRFs or eCRFs).

Adverse events will be recorded in an EPIC smartphrase contained within an EPIC clinic note. This will be transcribed into Oncore database. The information will include the unique subject identifier, event preferred term, CTCAE body system, date of occurrence, date of resolution; and type of resolution. All signs, symptoms, significant laboratory findings, AND diagnoses should be recorded, regardless of relationship, except as described in this document. A single “overarching” diagnosis should not be solely entered as the adverse event term in lieu of the full list of observed signs, symptoms, and significant laboratory findings, which may include the diagnostic preferred term.

Types of resolution are:

- “Resolved,” ie, to Grade 0 (or baseline if a pre-existing condition)
- “Continuing” and stable (includes downgrades from a higher grade to a lower grade)
- “Deceased” (due to any cause while on-study)
- Lost-to-follow-up.
- **NOTE:** “Hospitalized” is not an outcome.

Any pre-existing condition that worsens in severity/grade or frequency should be recorded as a new adverse event, except as described in this document.

7.5. Adverse Events of Special Consideration

7.5.1. Second vs Secondary Malignancy

7.5.1.1. Second Malignancy

A second malignancy is one unrelated to the treatment of a prior malignancy (and is NOT a metastasis from the initial malignancy). A second malignancy is by definition a serious adverse event (SAE), and will be recorded and reported accordingly.

7.5.1.2. Secondary Malignancy

In the context of a clinical study, a secondary malignancy is a cancer caused by chemotherapy, radiation, or the investigational agent/intervention. A secondary malignancy is not considered a metastasis of the initial neoplasm, but nonetheless, a secondary malignancy is by definition a serious adverse event (SAE), and will be recorded and reported accordingly. Secondary malignancies are usually described as one of the following:

- Leukemia secondary to oncology chemotherapy [eg, acute myelocytic leukemia (AML)]
- Myelodysplastic syndrome (MDS)
- Treatment-related secondary malignancy

By definition, secondary malignancies are adverse events that are both serious and related to the research, and should be anticipated to be an Unanticipated Problem (UP) and reported accordingly. If also determined to be related to the study treatment, and not described by the Investigator's Brochure or package insert as known to be associated with the study agent, the secondary malignancies may also necessitate Expedited Reporting to FDA, eg, an IND Safety Report to the IND.

7.5.2. Progressive Disease

Progressive disease will be reported by the clinical signs or symptoms of disease progression. If the event is Grade 5 fatal and signs/symptoms of disease progression are not available / informative for the event, the CTCAE v5.0 preferred term "Disease Progress" may be used.

7.5.3. Other Adverse Events of Special Interest

Adverse events of special interest (AESI) are selected non-serious and serious AEs that must be reported regardless of relationship to study treatment. Refer to Table 8 for the AESIs identified for this study. AESIs will be followed until resolution or return to baseline.

Serious AESIs will be reported to SpringWorks Safety at ([contact]) according to procedures and timeline (Section 7.6)

Non-serious AESIs must be reported to SpringWorks Safety at [contact] as soon as possible, but no later than 30 calendar days of awareness.

Following medical evaluation, SpringWorks may request study site to provide supplemental information (such as medical history, concomitant medications, investigations, etc.) about the event. Please note this table lists known AESI; additional events may be identified during the course of the study.

Table 8. Adverse Events of Special Interest

Elevated Liver Enzymes (reported as AESI if Grade ≥ 2, per CTCAE v. 5)
1. AST
2. ALT
3. Alkaline Phosphatase
4. Total bilirubin
Drug Reactions, any Grade
1. Allergic reaction
2. Anaphylaxis
3. (Drug) Hypersensitivity
Ovarian Dysfunction, any Grade¹
1. Ovarian dysfunction
2. Ovarian Disorder
3. Amenorrhea
4. Oligomenorrhea
5. Premature Menopause
6. Ovarian failure
Non-Melanoma Skin Cancer, any Grade, and Pre-cancerous Skin Lesions, any Grade
1. Basal cell carcinoma
2. Squamous cell carcinoma (of skin)
3. Keratoacanthoma
4. Actinic keratosis

¹ Females reporting AEs / AESIs / SAEs of ovarian dysfunction will have hormone levels assessed every 3 months until event resolution (or for at least 90 days after discontinuing study treatment).

7.6. Adverse Event Reporting

Reportable adverse events, based on relatedness (attribution) to the study agent; expectedness, severity (Grade 1 to 5), seriousness (Yes/No), or any other aspect of the investigation, will be reported as described below.

- Whenever possible, diagnoses should be given when signs and symptoms are due to a common etiology (eg, cough, runny nose, sneezing, sore throat; and head congestion should be reported as "upper respiratory infection").

- Serious adverse events (SAEs) per the definition at [21CFR§312.32](#) will be reported to the sponsor-investigator (IND holder), [name], **within 24 hours of the knowledge of the event.**
- SAEs will be reported by the IND-holder to the study drug supplier / funding source SpringWorks on a MedWatch Form FDA 3500A for an SAE initial and follow-up case (as defined later in this Section 3.2) for a 7 day or 15 day expedited report to SpringWorks at the same time of reporting to the regulatory authorities; and submit all SAE initial and follow-up cases that do not qualify for reporting to regulatory authorities as an expedited report to SpringWorks within 30 calendar days from the date of investigator awareness. Reports should be completed and submitted by email to [contact] and/or [contact].
- SAEs will be reported to the SCI Data and Safety Monitoring Committee (DSMC) by submission to CCTO-Safety. The event must be described on either the SCI SAE form (see references in Appendix A), or a study-specific form. If applicable, the Form FDA 3500A (see Section 7.6) for mandatory IND Safety Reports may be substituted. The report will be sent by secure email to [contact] at the time of the **first** notification to any of the drug supplier / funding source, SpringWorks; the IRB of record; or the IND (ie, FDA). The SAE form must be signed by the investigator. CCTO-Safety will process the SAE report into OnCore, and the DSMC will review the event. See the SCI Data Safety and Monitoring Plan (DSMP).
- SAEs per [21CFR§312.32](#) will be reported by the IND-holder, [name], to the IND under which this study is being conducted within 7 days (for a life-threatening or fatal event) or 15 days (for other SAEs) of the IND-holder's determination that the SAE meets the criteria for an IND safety report, ie, the event was serious, unexpected, and at least possibly-related to the study drug [a serious, unexpected, suspected adverse reaction (SUSAR)]. IND Safety Reports will be submitted to the IND using the MedWatch Form FDA 3500A for mandatory reporting.

Do not send IND Safety Reports to the MedWatch fax number, ie, the number for voluntary post-marketing safety reporting.

IND Safety Reports will be submitted to either the address specified in the IND Study May Proceed letter, any other address specified by the IND reviewers, or via the Electronic Submissions Gateway (contact [contact] for electronic submission assistance).

- All SAEs per protocol will be reported will be reported to the IRB of record in the Continuing Review, and/or the Final Report. IRB reporting format can be as an event line listing (such as the Adverse Event log), or as an aggregate listing or summary (such as an IND Annual Report or SAE listing for ClinicalTrials.gov).

- All **Unanticipated Problem (UPs)** associated with the use of a drug, biologic, or device will be reported as follows.
 - Note that for the purposes of Stanford IRB Unanticipated Problem reporting, subjects are considered to be study participants when consented, ie, events during screening and/or pre-treatment through that subject's official end of study participation may qualify as reportable.
 - To the Stanford IRB, by the Stanford Protocol Director, if an adverse event meets the Stanford IRB's current definition of an Unanticipated Problem (UP) as specified by the IRB document "Events and Information that Require Prompt Reporting to the IRB" (GUI-P13), per the timeframes defined therein. See also Section 9.3 Data and Safety Monitoring Plan. In addition to event triggered expedited UP reports, all UPs should be summarized in the Continuing Review, with, as applicable, a discussion of any change in assessment of risk (ie, different than previously described).
 - To the SCI Data and Safety Monitoring Committee (DSMC), by submission to CCTO-Safety / OnCore as an SAE (see SAE reporting to DSMC above. See also the SCI DSMP).

Serious adverse events (SAEs) will be reported to the IRB of record and to the DSMC in accordance with the applicable guidelines and regulations.

All serious adverse events (SAEs) will be followed for 30 days after the last dose of the study drug nirogacestat, or until the SAE(s) is/are resolved or stable, whichever is longer. Pregnancies will be followed until term. See also Section 3.8, 5.6, 6.0, and 7.2.4.

Adverse events that are serious and unexpected suspected adverse reactions, ie, are possibly, probably, or definitely-related to the study drug nirogacestat will be reported (on a MedWatch 3500A form) to the FDA via IND Safety Report [[21CFR§312.32](#)] within 15 calendar days, or within 7 calendar days if the event is an unexpected fatal or life-threatening suspected adverse reaction. The IND annual report will include summaries of the collected AEs, as specified by [21CFR§312.33](#).

7.7. Adverse Event Records

The investigator will retain adverse event source data, supporting documentation of attribution and seriousness, and copies of official adverse event reports or SAE CRFs, as well as documentation of informal communications (such as telephone calls or emails) in accordance with the current version of Stanford School of Medicine standard operating procedure SOP-005 "Identifying and Reporting Adverse Events" (see references in Appendix A).

